### **3. GENERAL CONSIDERATIONS FOR DATA ANALYSES**

Analysis results will be presented using descriptive statistics. For categorical variables, the number and percentage of subjects in each category will be presented; for continuous variables, the number of subjects (n), mean, standard deviation (SD) or standard error (SE), median, first quartile (Q1), third quartile (Q3), minimum, and maximum will be presented.

By-subject listings will be presented for all subjects in the All Enrolled Analysis Set unless otherwise specified, and sorted by subject identification (ID) number, visit date, and time (if applicable). Data collected on log forms, such as AEs, will be presented in chronological order within subject. The part (e.g. Part 1 or Part 2) under which subjects were enrolled will be included in the listings.

In general, age (in years) on the date of the first dose of study drug will be used for analyses and presentation in listings. If a subject was not dosed with study drug, the date of enrollment will be used instead of the first dose date of study drug. For screen failures, age as calculated on the date that informed consent was signed will be used.

In general, permanent discontinuation of study drug refers to premature discontinuation of study drug or completeness of study drug.

#### **3.1. Analysis Sets**

Analysis sets define the subjects to be included in an analysis. Analysis sets and their definitions are provided in this section. The analysis set will be identified and included as a subtitle of each table, figure, and listing. A summary of the number and percentage of subjects in each analysis set will be provided overall and by Parts 1 and 2.

##### **3.1.1. All Enrolled Analysis Set**

The All Enrolled Analysis set includes all subjects who enrolled into the study. This is the primary analysis set for by-subject listings.

##### **3.1.2. Full Analysis Set**

The Full Analysis Set (FAS) will include all the subjects who were enrolled and received at least one dose of study drug. For the FAS, all efficacy data will be included, unless specified otherwise. The FAS is the primary analysis set for the efficacy analyses.

Subjects meeting the following criteria will be excluded from the FAS:

- Subjects who took Stribild or Descovy as part of the baseline antiretroviral (ARV) regimen and thus violated the inclusion criterion.

### **3.1.3. Safety Analysis Set**

The Safety Analysis Set includes all enrolled subjects who took at least 1 dose of study drug. This is the primary analysis set for safety analyses.

### **3.2. Strata and Covariates**

There is no stratification for enrollment.

### **3.3. Subject Subgroup Grouping**

The subjects will be grouped by Part 1, Part 2 and overall.

### **3.4. Multiple Comparisons**

Adjustments for multiplicity will not be made, because no formal statistical testing will be performed in this study.

### **3.5. Missing Data and Outliers**

#### **3.5.1. Missing Data**

A missing data point for a given study visit may be due to any of the following reasons:

- A visit occurred in the window but data were not collected or were unusable
- A visit did not occur in the window
- A subject permanently discontinued from the study before reaching the window.

In general, values for missing data will not be imputed, unless otherwise specified.

For missing last dosing date of study drug, imputation rules are described in Section 3.5.1 and the SAP [Appendix 5](#). The handling of missing or incomplete dates for AE onset is described in Section 7.1.6.2, and for concomitant medications in Section 7.5.2 as well as the SAP [Appendix 5](#).

#### **3.5.2. Outliers**

Outliers will be identified during the data management and data analysis processes, but no sensitivity analyses will be done to evaluate the impact of outliers on efficacy or safety outcomes, unless specified otherwise. All data will be included in the analyses.

### 3.6. Data Handling Conventions and Transformations

Laboratory data that are continuous in nature but are less than the lower limit of quantitation or above the upper limit of quantitation will be imputed as follows except for urine creatinine:

- A value that is 1 unit less than the limit of quantitation (LOQ) will be used for calculation of descriptive statistics if the datum is reported in the form of “< x” (x is considered as the limit of quantitation). For example, if the values are reported as < 20 and < 5.0, values of 19 and 4.9 will be used for calculation of summary statistics, respectively. An exception to this rule is: for values reported as < 1 or < 0.1, a value of 0.9 or 0.09, respectively, will be used for calculation of summary statistics.
- A value that is 1 unit above the LOQ will be used for calculation of descriptive statistics if the datum is reported in the form of “> x” (x is considered as the LOQ). Values with decimal points will follow the same logic as above.
- The LOQ will be used for calculation of descriptive statistics if the data is reported in the form of “≤ x” or “≥ x” (x is considered as the LOQ).

For urine creatinine, value of “< 1” is handled as a missing value in its summary and the calculation of related ratios.

### 3.7. Analysis Visit Windows

#### 3.7.1. Definition of Study Day

**Study Day 1** is defined as the day when the first dose of study drug (ie, E/C/F/TAF) was taken, as recorded on the Study Drug Administration eCRF form.

**Study Days** are calculated relative to Study Day 1. For events that occurred on or after Study Day 1 date, study days are calculated as (visit date minus date of the first dose plus 1). For events that occurred prior to Study Day 1, study days are calculated as (visit date minus date of the first dose).

**Last Dose Date** is the latest nonmissing end date of study drug (E/C/F/TAF) recorded on the Study Drug Administration eCRF form with “Study Drug Permanently Withdrawn” box checked for subjects who prematurely discontinued study drug or who completed study drug according to Study Drug Completion eCRF.

If the date of last dose is missing (eg, only year of last dose is known or completely missing due to lost to follow-up) for subjects who prematurely discontinued study drug, or for subjects who completed study drug, the latest of nonmissing study drug start dates and end dates, the clinic visit dates, and the laboratory visit dates excluding the date of 30-day follow-up visit will be used to impute the last dose date. For other partial missing last dose date, please see SAP [Appendix 5](#) for details.

**Last Study Date** is the latest of nonmissing study drug start dates and end dates, the clinic visit dates, and the laboratory visit dates including the 30-day follow-up visit date for subjects who prematurely discontinued study or who completed study according to Study Completion eCRF.

**Baseline Value** for HIV-1 RNA, CD4+ cell count, CD4%, hematology, chemistry, urinalysis and urine chemistry laboratory tests, fasting glucose and lipid panels, eGFRCG, cystatin C testing, vital signs and weight, safety electrocardiogram (ECG), Visual Analogue Scale (VAS) Adherence Questionnaire, Medical Outcome Study Short Form-36 Questionnaire (SF-36), HIV Treatment Satisfaction Questionnaire (HIVTSQ) (Status at Day 1 only), Functional Assessment of Chronic Illness Therapy – Fatigue (FACIT-F), and EQ-5D is defined as the last nonmissing value obtained on or prior to Study Day 1.

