6.3. Treatment Assessments

6.3.1. Treatment Visits (Weeks 4 – 48)

The following evaluations are to be completed at the end of Weeks 4, 8, 12, 16, 24, 36 and 48 unless otherwise specified.

All study visits are to be scheduled relative to the Day 1 visit date. Study visits are to be completed within ± 2 days of the protocol-specified visit date through Week 16 and completed within ± 6 days of the protocol-specified visit date through Week 36, unless otherwise specified. The visit window at Week 48 will be ± 6 weeks of the protocol-specified visit date, which coincides with the Week 48 statistical analysis window for HIV-1 RNA. For the purposes of scheduling the Week 48 visit, a ± 6 day window of the protocol-specified visit date should be used.

Regularly scheduled evaluations will be made on all subjects whether or not they continue to receive study drug.

Note: At the Week 16 visit, the only assessments to be completed are:

- Review of AEs and changes in concomitant medications
- Blood sample collection for the following laboratory analyses:
 - Plasma HIV-1 RNA
 - Plasma sample storage for safety and virology testing
- Document study drug dispensation and accountability for all study drug dispensed.
- Questionnaire: Subject is to read questionnaire by her/himself and write/mark answers directly onto questionnaire.
 - Visual Analog Scale (VAS)

For all other visits, please complete the following:

- Review of AEs and changes in concomitant medications
- Complete physical examination (**Weeks 24 and 48**) (urogenital/anorectal exams will be performed at the discretion of the Investigator)
- Symptom-directed physical examination as needed (**Weeks 4, 8, 12 and 36**)
- 12-lead ECG performed supine (**Week 48 only**)
- Vital signs (blood pressure, pulse, respiration rate, and temperature), including weight
- Urine collection for the following laboratory procedures:
 - Urinalysis and urine chemistry
 - Urine pregnancy test (females of childbearing potential only); positive urine pregnancy tests will be confirmed with a serum test. If the test is positive, the subject will be discontinued.
 - Urine sample storage for possible additional clinical testing
- Blood sample collection for the following laboratory analyses:

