6.4. Post-treatment Assessments

6.4.1. Early Study Drug Discontinuation (ESDD) Visit

If a subject discontinues study drug prior to the Week 48 visit, the subject will be asked to return to the clinic within 72 hours of stopping study drug for the ESDD visit. The subject will be asked to continue attending the scheduled study visits through Week 48.

At the ESDD Visit, any evaluations showing abnormal results indicating that there is a possible or probable causal relationship with the study drug, will be repeated weekly (or as often as deemed prudent by the Investigator) until the abnormality is resolved, returns to baseline, or is otherwise explained.

The following evaluations are to be completed at the Early Study Drug Discontinuation Visit:

- Review of AEs and changes in concomitant medications
- Complete physical examination (urogenital/anorectal exams will be performed at the discretion of the Investigator)
- 12-lead ECG performed supine
- Vital signs (blood pressure, pulse, respiration rate, and temperature), including weight
- Urine collection for the following laboratory procedures:
 - Urinalysis and urine chemistry
 - Urine pregnancy test (females of childbearing potential only); positive urine pregnancy tests will be confirmed with a serum test.
 - Urine sample storage for possible additional clinical testing
- Blood sample collection for the following laboratory analyses:
 - Chemistry profile: alkaline phosphatase, AST, ALT, total bilirubin, direct and indirect bilirubin, total protein, albumin, bicarbonate, BUN, calcium, chloride, creatinine, glucose, potassium and sodium
 - Estimated GFR, according to the Cockcroft-Gault formula for creatinine clearance
 - Hematology profile: CBC with differential and platelet count
 - Plasma HIV-1 RNA
 - CD4+ cell count
 - Plasma sample storage for safety and virology testing
 - **CCI**

- Questionnaire: Subject is to read questionnaire by her/himself and write/mark answers directly onto questionnaire.
 - Visual Analog Scale (VAS)
 - HIV-TSQc
- HIV-1 genotype/phenotype resistance testing for subjects with unconfirmed virologic rebound with HIV-1 RNA value ≥ 50 copies/mL
- Questionnaire: Subject is to read questionnaire by her/himself and write/mark answers directly onto questionnaire.
 - HIV Treatment Satisfaction Questionnaire Change (HIV-TSQc)
- Study drug accountability

6.4.2. 30-Day Follow-up Visit

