6.8.2. Resistance Analysis at Subjects Last Visit

Subjects with HIV-1 RNA $<$ 50 copies/mL could experience unconfirmed blips of HIV-1 RNA \geq 50 copies/mL at their last study visit. Such subjects will be analyzed for resistance if the unconfirmed rebound happens at Week 48 or at the last visit while taking study drug (or within 72 hours of discontinuation of study drug).

Figure 6-1. Management of Virologic Failure

- a If virologic rebound is not confirmed, the subject will remain on the study drug.
- b If virologic rebound is confirmed, and the HIV-1 RNA is ≥ 50 copies/mL, the HIV-1 genotype and phenotype (reverse transcriptase, protease and integrase resistance) will be analyzed.
- c Based on the results of the genotype/phenotype assays, the subject will remain or discontinue study drug. If genotyping/phenotyping assay fails, a new ARV regimen may be configured at the discretion of the Investigator in consultation with the Medical Monitor.
- d If no resistance detected, HIV-1 RNA will be repeated (2-4 weeks later). Investigator reviews study drug continuation/discontinuation options and discusses with Medical Monitor prior to discontinuation.
- e A new ARV regimen will be configured, at the Investigator's discretion, and the subject will remain in the study.

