22) For safety ECGs at postbaseline visits, the most conservative (worst) value within the window will be selected, eg, abnormal will be selected over normal for safety ECG or clinical significant abnormal will be selected over not clinical significant abnormal if there are multiple abnormal findings.

23) Last Dose Date and Last Study Date

a) Last Dose Date (ie, TRTEDTC or TRTEDT in ADSL)

- For subjects with a partial last dosing date (ie, month and year of last dose are known), use the max (the dispensing dates of study drug bottles, study drug start dates and end dates, imputed last dose date [day imputed as 15]) as the final imputed last dose date. (However if dispensing date's month is after last dose date's month, data query is needed.)
- If subject died and the death date is complete (ie, not partial date) and before the imputed last dose date, the complete death date should be used as the imputed last dose date.
- If the date of last dose is missing (eg, only year of last dose is known or completely missing due to lost to follow-up), use the maximum of study drug start dates and end dates, clinic visit dates (i.e., visit dates from vital sign and ECG forms), and laboratory visit dates excluding the 30-day follow-up visit to impute the last dose date.

- b) Last Study Date is the maximum of nonmissing study drug start dates and end dates, clinic visit dates (i.e., visit dates from vital sign and ECG forms) and laboratory visit dates, including the 30-day follow-up visit date for subjects who prematurely discontinued study or who completed study according to study completion eCRF. Please note, if study drug start date or end date is partially missing, the imputed date (day imputed as 15) will be used. If subject died and the death date is complete (ie, not partial date) and before the imputed last study date, the complete death date should be used as the imputed last study date.

24) Toxicity Grades:

- a) For toxicity grade summary, we will include all postbaseline graded results up to 30 days after last dose of study drug, not just those at summarized visits.
- b) For hematuria grading, if the laboratory reports urine blood using the plus system (+1, +2, etc) and also provides quantitative results on reflex (ie, urine RBC), summarize only the grade of the urine RBC results, but list both grades of urine blood and urine RBC.

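### A wholly missing or year-only last dose date is imputed as the latest visit, so off-drug HIV-1 RNA could be counted as on-treatment in the snapshot (rare; primary Week 12 PVR not affected)

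*SAP*

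**What the plan says.** SAP 3.7.1 covers subjects who stopped or completed study drug and whose last dose date is absent or known only by year. The imputed date is the latest of the drug start and end dates, the clinic visits and the laboratory visits: "the laboratory visit dates excluding the date of 30-day follow-up visit will be used to impute the last dose date". Appendix 5 item 23(a) gives the programming form, drawing on "clinic visit dates (i.e., visit dates from vital sign and ECG forms), and laboratory visit dates excluding the 30-day follow-up visit". Only one cap is written there: where a complete death date is earlier, "the complete death date should be used as the imputed last dose date". If month and year are known, a separate day-15 rule applies and clinic and laboratory visits are not used.

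The protocol keeps visits going after drug stops. Section 6.4.1: "The subject will be asked to continue attending the scheduled study visits through Week 48". Section 6.3.1: "Regularly scheduled evaluations will be made on all subjects whether or not they continue to receive study drug". Appendix 2 schedules HIV-1 RNA at every visit. Note e to Figure 6-1 has a new regimen set up after virologic failure "and the subject will remain in the study". Under section 6.4.2, a subject who attends at least one visit after the ESDD visit does not need the 30-day follow-up.

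SAP 6.2.2.3 and Appendix 5 item 25 treat HIV-1 RNA as on-treatment up to one day after the last dose date. In 6.2.2.3 the discontinuation categories apply only when no on-treatment value lies in the analysis window.

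**The concern.** The latest visit is a fair stand-in for the last dose when visits end with treatment. Here they need not. The one visit that the rule leaves out, the 30-day follow-up, is the one that subjects in continued follow-up are excused from, so the exclusion does not protect against the problem. SAP 3.7.1 defines the last study date by the same formula with the 30-day visit added. For a subject who stops drug, stays in follow-up and has no 30-day visit, the imputed last dose date and the last study date therefore coincide.

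A last dose date that is too late relabels off-drug values as on-treatment. In the snapshot, such a value in the window takes precedence over the reason for stopping. Suppression after E/C/F/TAF was stopped, possibly on another regimen, could then be credited to E/C/F/TAF. The same date also feeds CD4+ count and CD4% (SAP 6.2.2.6, 6.2.2.7), on-treatment proteinuria (7.3.3, 7.3.4), exposure and time to drug discontinuation (4.2.1), the joint table of virologic failure and drug discontinuation (6.1.1.2) and the 30-day safety window (section 7).

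**Working it through.** **The plan's own figures.** The documents give no figure for this rule. The stated confidence-interval half-widths reproduce: 1.96 × √(0.90 × 0.10 / 100) = 5.88% (stated 5.9%) and 1.96 × √(0.95 × 0.05 / 64) = 5.34% (stated 5.3%). Neither depends on the last dose date. The sample size of 64 comes from SAP 1.3.

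**Applying the rule to two constructed subjects.** Inputs from the SAP are the Table 3-1 windows (Week 12: Days 71–98; Week 24: Days 141–210; Week 48: Days 295–378) and on-treatment = last dose date + 1 day. Assumed inputs are a true last dose on Day 100, an ESDD visit on Day 102 (within the protocol's 72 hours), scheduled visits to Day 336 and no last dose date recorded.

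- Subject A stops for a reason other than adverse event, death or lack of efficacy, and stays below 50 copies/mL.
- Subject B has 120 copies/mL on Day 84 and 150 on Day 102, stops for lack of efficacy, and is below 50 from Day 112 on a new regimen.

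The SAP rule imputes Day 336 for both, which is 336 − 100 = 236 days late.

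| Subject | Snapshot visit | SAP rule (Day 336) | Capped at ESDD (Day 102) |
|---|---|---|---|
| A | Week 12 | < 50 | < 50 |
| A | Weeks 24 and 48 | < 50 | No virologic data |
| B | Week 12 | ≥ 50 | ≥ 50 |
| B | Weeks 24 and 48 | < 50 | ≥ 50 (lack of efficacy) |

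Using the true Day 100 in place of the cap gives the same classifications as the last column.

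**Size in the snapshot.** One subject is 1/64 = 1.56 percentage points. The number affected is not in the documents, so 1 to 3 is an assumption, as is the starting count of 61. Exact 95% intervals (the SAP's method for the snapshot) at n = 64:

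| Successes | Rate | Exact 95% CI |
|---|---|---|
| 61 | 95.3% | 86.9–99.0 |
| 60 | 93.8% | 84.8–98.3 |
| 59 | 92.2% | 82.7–97.4 |
| 58 | 90.6% | 80.7–96.5 |

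**Size in exposure.** At the extreme, a subject who stops near Week 4 and attends to Week 48 would have exposure overstated by about 48 − 4 = 44 weeks.

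**Primary endpoint.** SAP 6.1.1.1 classifies by confirmed rebound, or by a last value ≥ 50 copies/mL followed by premature discontinuation of the study. It has no on-treatment restriction. Subject B is a pure virologic failure at Week 12 whichever last dose date is used, because the Day 84 value is confirmed on Day 102.

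**Does another rule block this?** Appendix 5 item 26(b) deals only with an HIV-1 RNA value on the day a new antiretroviral starts; it does not cap the last dose date. When only the year is known, nothing keeps the imputed date within that year.

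**The case against.** The strongest reply is that the trigger and the harm seldom meet. The SAP's own example of a missing date is loss to follow-up, where few later visits exist and the last contact is a reasonable bound. The harmful case needs a subject who keeps attending but whose stop date is unknown even to the month. The documents work against that: an ESDD visit with drug accountability (Protocol 6.4.1), start and end dates of drug in the source records (9.1.5), data queries (9.1.6) and query resolution before the final analysis (SAP 2.3). Discontinuations and non-study antiretrovirals are also listed (SAP 4.1.2, 6.2.2.2, 7.5.1), so an overlap could be noticed. The snapshot is labelled a sensitivity analysis.

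All of this stands, and it makes the point small. The constructed subjects show what the rule does when used, not that it will be used often. But listings do not correct a derived date, and no text limits the rule as written.

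A reader might infer that off-drug subjects are usually on a new regimen. The documents show that this can happen; they give no frequency.

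**Conclusion.** The imputation rule gives a wrong date when it is applied to a subject who stopped drug early and stayed in follow-up. It could then turn a snapshot failure or a no-data outcome into a success at a later visit, including after stopping for lack of efficacy. The size is 1.6 percentage points per affected subject at n = 64, slightly more if exclusions make the Full Analysis Set smaller. The number of such subjects is not given and is expected to be very small, possibly zero.

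A reader might infer that the primary result is at risk. The SAP does not support that: its Week 12 pure virologic response does not use the last dose date. (Protocol 8.4.1 adds a condition of remaining on study treatment; SAP 6.1.1.1 does not carry it.) Nor does the problem reach every early discontinuation: a last dose date known to the month or better never enters this rule.

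**What to change.** In SAP 3.7.1, for subjects who discontinued study drug early, cap the imputed date at the earlier of the ESDD visit date and the day before the first new non-study antiretroviral. Where only the year is known, also cap it at the end of that year. Exclude visits after ESDD from the dates used. Make the same change in Appendix 5 item 23, and list every subject with an imputed last dose date. If there are none, one sentence in the study report closes the point.

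Because on-treatment runs to one day after the last dose, a value drawn on the day the new antiretroviral starts stays in, which agrees with item 26(b). I would not add a cap based on tablets dispensed: a subject who missed doses can still be taking drug after the nominal run-out, and genuine on-treatment data would be lost. SAP 3.5.1 also cites itself for this rule and should point to 3.7.1.

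The cost is about one sentence in each of two places and one short listing, using data already collected. The downside is that the capped date may be slightly early or late for an individual, for example up to three days late when ESDD is the cap and the visit is on time. A subject with neither an ESDD visit nor a recorded new antiretroviral would still fall back on the latest visit, and the listing would show this.
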